1.2 Rationale for study design, doses and control groups

This phase 3 study was intended to be included in applications for marketing authorization in the countries where the study is performed. ZS was approved in China for hyperkalemia based on overseas data at the end of 2019, now this is a post-approval commitment study for China.

A double-blind, placebo-controlled, randomized study represents the optimal design for obtaining unbiased estimates of treatment group differences for a new drug under development. Recognizing that all patients will receive active treatment during the open-label initial phase, combined with the fact that all patients will be monitored in the clinic for at least 4 hours after the initial dose of ZS, the level of hyperkalemia that could be included is not limited.

The randomized portion of the study (the 28-day randomized treatment study phase) is designed to assess whether extended administration of ZS maintains control of S-K values and to demonstrate that hyperkalemia recurs once ZS is withdrawn. Such design represents state-ofthe-art in demonstrating the need for ongoing longer-term treatment of a new drug under development. A 28-day randomized treatment study phase is selected as a compromise between ensuring a sufficiently long treatment period to demonstrate that ZS can maintain normokalemia over extended time, while not exposing patients with a potentially life-threatening condition to extended treatment with placebo. Eligibility for the open-label initial phase, eligibility for the 28-day randomized treatment study phase, and potassium-related stopping criteria are based on i-STAT measurements as these decisions need to be made in 'real-time' due to the risk of potentially life-threatening cardiac arrhythmias associated with severe hyperkalemia or hypokalemia. However, all endpoint analyses will be based on standardized S-K measurements analyzed at a central laboratory. For treatment decisions (i.e., S-K values on i-STAT < 3.5mmol/L), a second i-STAT sample will be taken 10 minutes after the initial abnormal sample to ensure that treatment is only changed once hypokalemia is confirmed. For a treatment decision to be made, both samples, taken 10 minutes apart, need to be below 3.5 mmol/L.

[figure not shown]

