- Patients with i-STAT potassium levels < 6.1 and ≥ 4.0mmol/L at the 4 hour (± 15 minutes) post Dose 1 blood draw will be sent home with instructions on how to take the IP. They will be requested to fill out a dosing schedule card indicating when they took the IP. The patient will return to the clinic the following morning for the open-label initial Phase Day 2 (Visit 4)
- Patients with i-STAT potassium ≥ 6.1 or < 4.0 mmol/L at the 4 hour post Dose 1 blood draw will stay in the clinic and take the second dose of study drug approximately 4-hours after the first dose. They will then remain in the clinic an extra 90 minutes (± 15 minutes) after taking the second dose when another blood sample for potassium determination (i-STAT and Central Laboratory will be collected and an ECG will be recorded).
- If i-STAT potassium levels are > 6.2 mmol/L as determined by the i-STAT at the 90minute post Dose 2 blood draw, the patient will be discontinued from the study. Patients will return to the clinic 7 (±1) days later for an EOS visit.
- If i-STAT potassium levels are ≤6.2 mmol/L and the ECG does not show any of the ECG withdrawal criteria, the patient will be sent home with the third dose of study drug and the dosing card and return to the clinic in the morning of the open-label initial phase Day 2 (Visit 4).
- See Section 7.2 regarding how to handle patients with potassium < 3.5mmol/L.

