
"Open-label phase mean change from baseline of S-K to the end of OLP after first dose of ZS 10g".

To clarify the definition of the full analysis set in the open label initial phase, a subject is considered to have been registered into the OLP if they received at least 1 dose of study medication in the open label initial phase.

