3.2.1.1 Full analysis set in Open-label initial phase (FAS-OLP)

For the open-label initial phase (OLP), the full analysis set will include all subjects who received at least 1 dose of study medication in the open-label initial phase.

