
2. Potassium is measured predose and 1 hour post dose. The predose measure is considered as the 24-hour measurement for all analyses. Patients who achieve normokalemia at 24 hours will proceed to the Randomization (RTP-Day 1) visit.

3. Potassium is measured predose and this measure is considered as the 48-hour measurement for all analyses.

4. End of OLP (24 hours or 48 hours) the latest treatment day of open label initial phase only for patients who complete 24 hours or 48 hours OLP treatment.

5. End of Study Visit (OLP-Day 9) in open label initial phase only for patients NOT entering the 28-day randomized treatment study phase and occurs 7±1 day after the last administration of IP.

6. End of Study Visit (RTP-Day 35) occurs 7±1 day after last planned administration of IP in RTP.

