Secondary	1- Proportion of subjects who achieve normokalemia (3.5 – 5.0 mmol/L) during and at the end of OLP (classification of each screened subject as	FAS-OLP	Treatment policy: intercurrent events ignored. This policy will be used for all four of the endpoints in this section.	 1- Probability of subjects achieving normokalemia, at 24 h and at the end of OLP, estimated as proportion of responders, with 95% two-sided Clopper-Pearson exact CIs. 2- The time effect derived from 	4.2.2.4		

STATISTICAL ANALYSIS PLAN D9480C00001 – ed. 3.0

Statistical category	Endpoint	Analysis set	Intercurrent event strategy	Population level summary (analysis)	Details in section
	 either a "responder" or a "non-responder") 2- Exponential rate of change in S-K levels during OLP 24 hours post-dose 3- Mean change (absolute and percent change) in S-K level at all post-dose time intervals during OLP 4- Time to normalization in S-K levels during OLP 			a longitudinal mixed model including all SK measurements up to 24 hours post-dose 3- Mean change (absolute and percent change) in S-K level from baseline to each of the planned measurement occasions during OLP, as well as end of OLP, analyzed using one sample, two-sided t-tests 4- The CDF of time to S-K normalization estimated using Kaplan-Meier life table curves	
Supplementary	Proportion of subjects who achieve normokalemia without use of disallowed medications during and at the end of OLP	FAS-OLP	Composite strategy: Intercurrent event (use of disallowed medication) is included as part of a composite endpoint, where subjects can only be counted as a "success" (responder) if they did not receive any disallowed medication before the measurement occasion and if they are normokalemic (S-K between 3.5-5.0 mmol/L).	Probability of subjects achieving normokalemia without usage of disallowed medications, estimated as proportion of responders, with 95% two-sided Clopper- Pearson exact CIs.	4.2.2.5
Supplementary	Mean change in S-K level from baseline to 24h and end of OLP	FAS-OLP	Hypothetical strategy: measurements obtained post usage of disallowed medications are removed from the analysis	Mean change in S-K level from baseline to 24h and end of OLP, analyzed using one sample, two-sided t-tests	4.2.2.5
Supplementary	Exponential rate of change in S-K levels during OLP 48 hours	FAS-OLP	Treatment policy: intercurrent events ignored.	The time effect derived from a longitudinal mixed model including all SK measurements	4.2.2.5

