4.2.2 Secondary Endpoints for OLP phase

4.2.2.1 Definition

The secondary efficacy endpoints for OLP phase will include the following:

- 1. Proportion of subjects who achieve normokalemia during the OLP at 24 hours (OLP Day 2) and at the end of the OLP. Each subject is classified into a responder or a non-responder category (i.e. a 0-1 type of response for subjects who achieve normokalemia or subjects who do not achieve normokalemia), with a subject being a responder if they have S-K between 3.5 and 5.0 mmol/L, inclusive. The following 7 time points during the OLP phase will be considered:
 - OLP Day 1, at 1, 2 and 4 hours post first dose
 - OLP Day 2, pre-dose and 1 hour post dose
 - o OLP Day 3, pre-dose
 - End of OLP

Note: not all subjects will have OLP Day 2, 1 hour post dose and OLP Day 3 pre-dose visit.

2. Exponential rate of change in S-K levels (blood) at 24 hours during OLP

- 3. Mean change (absolute and percent (%) change) from baseline in S-K levels at all measured time intervals post-dose during OLP listed above.
- 4. Time to normalization in S-K levels (normalization defined as first time S-K levels between 3.5-5.0 mmol/L, inclusive, are achieved) during OLP

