4.2.2.4 Primary Analysis of Secondary Endpoints (OLP)

Descriptive statistics will be presented for S-K levels at baseline, OLP Day 1 (1, 2 and 4 hours post first dose) and OLP Day 2 (pre-dose and 1 hour post the first dose in the day), OLP Day 3 (pre-dose) and end of OLP, including the mean change (absolute and percent change) from baseline. In addition, a box plot of S-K values by timepoint will be presented.

Similarly, descriptive statistics tabulating the proportion of subjects who achieve normokalemia at each of the timepoints specified above will be presented.

Proportion of subjects who achieve normokalemia

The observed proportions of subjects achieving normokalemia at 24 hours (OLP Day 2) and end of OLP will be provided along with 95% two-sided Clopper-Pearson exact confidence intervals.

Exponential rate of change

The exponential rate of change in S-K levels will be derived from a longitudinal mixed model (SAS PROC MIXED, see Section 3.3.5) of log-transformed S-K levels during the OLP. Measurements up to and including 24 hours post-dose will be used as the response variable. The model will include OLP baseline eGFR, OLP baseline S-K values as well as age (<55, 55-64, >64 years), time (in hours) and baseline binary indicators for RAAS inhibitors, chronic kidney disease, heart failure, and diabetes mellitus as fixed effects terms. A random intercept and slope (for time) will be used in the model. The exponential rate of change will correspond

to the estimate of the parameter describing the SK decline over time, i.e. the slope in terms of log SK. It will be presented with corresponding standard error, 95% confidence interval and p-value.

Mean change (absolute and percent change) from baseline

For changes and percent changes from baseline in S-K levels at 24 hours (OLP Day 2) (and end of OLP, one sample, two-sided t-tests will be applied to test the null hypotheses that the means are equal zero. The estimates, corresponding SD, 95% 2-sided CI and p-values will be presented.

Time to normalization in S-K values

The time to normalization in S-K levels will be summarized using Kaplan-Meier life table curves and associated 95% CI points will be provided at 1, 2, 4, 24 and 48 hours post first dose of IP.. All S-K assessments during OLP will be used.

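### Confirmatory test 1 has no end-of-OLP value for dosed patients who stop before completing 24 or 48 h of open-label treatment

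*SAP*

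**What the plan says.** SAP Section 2 replaces the protocol's 48-hour endpoint for the first confirmatory test with "Open-label phase mean change from baseline of S-K to the end of OLP after first dose of ZS 10g". It is order 1 in the hierarchy (SAP 3.3.7, Table 3). Under SAP 4.2.2.4, "one sample, two-sided t-tests will be applied to test the null hypotheses that the means are equal zero".

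The time point is defined in SAP 3.3.3, Table 2 note 4, as "the latest treatment day of open label initial phase only for patients who complete 24 hours or 48 hours OLP treatment". SAP 3.3.2.2 agrees: end of OLP is 24 or 48 hours, depending on how long the phase lasted.

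The population and strategy are wider. For FAS-OLP, "the full analysis set will include all subjects who received at least 1 dose of study medication in the open-label initial phase" (SAP 3.2.1.1). The estimand table in SAP 4.2 gives "Treatment policy: intercurrent events ignored. This policy will be used for all four of the endpoints in this section". For the response endpoint, "Each subject is classified into a responder or a non-responder category" (SAP 4.2.2.1).

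The protocol allows stops before 24 hours. On Day 1, if i-STAT potassium exceeds 6.2 mmol/L at the draw 90 minutes after dose 2, "the patient will be discontinued from the study" (Protocol 4.3.1). Confirmed values below 3.0 mmol/L, cardiac or ECG criteria, and patient decision can also end treatment (Protocol 3.9).

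**The concern.** A patient who takes one or two doses and is stopped on Day 1 is in FAS-OLP and has S-K scheduled at 1, 2 and 4 hours. Patients kept in the clinic for the dose 2 check also have a sample 90 minutes after that dose. Note 4 nevertheless gives such a patient no end-of-OLP value, so the patient contributes nothing to test 1. Whether a value exists then depends partly on the potassium response itself. That conflicts with a strategy of ignoring intercurrent events in all dosed patients, and SAP Section 2 does not list a restriction to completers among its changes. The pathway is realistic, because Protocol 1.2 says that "the level of hyperkalemia that could be included is not limited".

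What is at stake is the estimated mean change attached to a confirmatory test.

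**Working it through.** **Step 1. Does any rule bring early stoppers back?**
- SAP 4.2.2.3 is the only missing-data rule for the OLP endpoints. It refers to SAP 3.3.5, which replaces a missing central-laboratory value with an adjusted i-STAT value from the same visit. With no end-of-OLP visit there is nothing to replace.
- Protocol 3.9 brings a patient stopped in this phase back only for the EOS visit, 7 ± 1 days after the last dose.
- SAP 4.2.3.2 counts a stop for i-STAT above 6.2 mmol/L at the 90-minute post dose 2 draw as an event, but under time to hyperkalemia in the randomised phase. In the protocol that draw is on OLP Day 1. No matching rule exists for the OLP endpoints, and the two places need to be reconciled.

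So nothing restores these patients to test 1.

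**Step 2. Who is affected?** Patients above 5.0 mmol/L on Day 3 have been through 48 hours, are sampled that morning and only then withdrawn (Protocol 4.3.3). They have a value. The loss is confined to stops before completion, and the only such stop for potassium non-response is the Day 1 rule above 6.2 mmol/L. Note 4 leaves open whether a patient with doses withheld for 3.0 to 3.4 mmol/L (Protocol 7.2) has completed treatment.

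**Step 3. Reproduce the plan's power figure.** Protocol 8.2 gives n = 280, a reduction of 1.05 mmol/L and power above 99%. The SD of the change is not given, so it is varied. For a one-sample two-sided t-test at 5%, the noncentrality is 1.05 × √n / SD.
- SD 0.50 (stated only for the primary endpoint): 1.05 × √280 / 0.50 = 35.1; power about 100%.
- SD 3.0: n = 280 gives 99.995%; n = 252 gives 99.98%.
- Power stays above 99% up to an SD of about 4.08 (n = 280) or 3.87 (n = 252).

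The stated figure reproduces, and losing up to 28 patients does not threaten the test.

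**Step 4. Effect on the estimate.** Let f be the share stopped early and c their mean change. Assume that completers average -1.05. The all-patient mean is -1.05 × (1 - f) + c × f.

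Two illustrative values of c are used: -0.2 for stops above 6.2 mmol/L (assumed), and -2.1 for stops below 3.0 mmol/L (5.1 at entry minus 3.0).

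| f (assumed) | c = -0.2 | c = -2.1 |
|---|---|---|
| 1% | -1.04 | -1.06 |
| 3% | -1.02 | -1.08 |
| 5% | -1.01 | -1.10 |

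If 3% stop, half of each kind: -1.05 × 0.97 - 0.2 × 0.015 - 2.1 × 0.015 = -1.053, practically the completer value.

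A harsher case counts k of 280 early stoppers as zero change: 1.05 × (280 - k) / 280 gives a fall of 1.03 (k = 6), 1.00 (k = 14) or 0.945 (k = 28). With SD 0.50 in the others, the t statistics are still 33.2, 31.0 and 27.8.

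**The case against.** Note 4 is a footnote to a visit-allocation table that applies when nominal visits are absent, the Day 1 stop is narrow, and the documents give no frequency for it. Early stoppers' data are also used elsewhere: time to normalization uses all open-label S-K and censors at the last value, and the exponential-rate model uses every measurement up to 24 hours. All of this stands, and it keeps the point small. It does not remove it, because the SAP offers no other definition of end of OLP for a patient stopped before 24 hours.

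A reader might infer three stronger things.

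- **That non-responders in general drop out.** They do not: the Day 3 non-responders are sampled and kept.
- **That the end-of-OLP response rate is inflated.** With 252 responders, removing k patients from the denominator would turn 252/280 = 90.0% into 252/274 = 92.0% (k = 6) or 252/266 = 94.7% (k = 14). The text points away from this. Each subject is classified, a responder must have S-K in range, and SAP 3.3 takes percentages of the population total unless otherwise stated. Nor should early stops be deducted from the protocol's 90%: that figure already applies to everyone entering the phase (250 / 0.90 = 278, stated as about 280).
- **That the bias must favour ZS.** Stops above 6.2 mmol/L presumably reflect smaller falls, so leaving them out flatters ZS. Stops below 3.0 mmol/L reflect large falls, and leaving them out does the reverse. ECG and patient-decision stops have no known direction.

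**Conclusion.** The inconsistency is real and limited to the mean change in confirmatory test 1. The SAP claims treatment policy on all dosed patients but defines the time point for completers only. Under the assumed 1% to 5% early stops, the estimate moves by about 0.01 to 0.05 mmol/L, in either direction according to the mix of reasons. The early-stop share, the values of c and the application of 1.05 mmol/L to completers are assumptions. Significance of test 1, and so passage to the rest of the hierarchy, is not in question. The response proportion needs an explicit statement only: the SAP implies non-responder status without saying so for a missing value, and SAP 4.2.2.4 speaks of observed proportions. This is worth correcting because it concerns a confirmatory estimate and costs little.

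**What to change.** 1. Replace note 4: for every FAS-OLP subject, end of OLP is the last S-K after the first open-label dose, before the first randomised dose and no later than OLP Day 3. The Day 3 limit is preferable to the SAP's on-treatment window (last dose plus 1 day). Under Protocol 7.2 a patient low on Days 1 and 2 may take no Day 2 dose and be assessed for randomisation on Day 3; the on-treatment window would discard that Day 3 value.
2. State in SAP 4.2.2.4 that the denominator is all FAS-OLP and that a subject who discontinues open-label treatment before the 24 or 48 h assessment is a non-responder. Add that doses withheld under Protocol 7.2 are not discontinuation.
3. Report the completer version of test 1 as supplementary.

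The cost is SAP wording and one derivation, using S-K that the protocol already schedules. The drawback is that a Day 1 stopper contributes a value from the first hours only. For these patients it is a last-available-value rule rather than strict treatment policy, which the SAP should say, and the reported mean change may shift slightly.

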3.3.4 Handling of Unscheduled Visits

Unscheduled visits are included in the method of assigning data to scheduled visits described in the rules in Section 3.3.3 above. Unscheduled visits are not included as a separate visit in the summary tables, but they will be included in all listings of study data.

3.3.5 Handling of Missing Serum Potassium (S-K) Data

The S-K levels used for all analyses will be based on the central laboratory (c-lab) measurements. If the S-K c-lab data points are missing, the i-STAT data will be used to replace missing data by adjusting for the average paired difference between the c-lab and i-STAT levels collected at the same visit and with the same calibration method for the potassium assay. If the time difference between the SK c-lab and i-STAT measurements is greater than 15 minutes, the SK measure for that time point will be set as missing.

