- 5. For women of Childbearing potential, using-HCG will be measured at clinic, using the tube provided by Central Laboratory.
- 6. All potassium samples are analyzed by i-STAT and by the Central Laboratory on all occasion. And haemolysed samples should not be sent to the Central Lab for potassium, the sample should be re-drawn to obtain a sample showing no haemolysis. For diabetic patients all blood potassium samples should be collected prior to insulin administration whenever possible.
- 7. If a scheduled clinic visit falls on a weekend or short public holiday during the 28-day randomized treatment study phase, the scheduled visit may take place either 1 day early or 1 day late (i.e., within±24 hours of the scheduled day) for the 28-day randomized treatment study phase Days 5, 8, 12, 15, 19, 22, 26 and 35, up to 2 days late for the 28-day randomized treatment study phase Day 2 or 2 days early for Day 29. If the Day 29 visit is conducted early, the patient must take IP through Day 28 per protocol.
- 8. The defined wider visit window can be applied, if patients, are not able to strictly follow the pre-specified visit schedules, due to a prolonged public holiday. If the wider visit windows are applied for a particular visit, it is important that visits before and after such a visit also follows the wider visit windows. This will only apply during prolonged public holidays. Patients are expected to follow the pre-specified visit schedule once the prolonged holiday period is over.
- 9. EOS occurs 7 ± 1 day after the last administration of IP.
- 10. Access IVRS/IWRS on visit indicated or if patient permanently discontinues dosing before the end of the 28day randomized treatment study phase.
- 11. Due to a public holiday, patients may visit the clinic up to two days after the pre-specified visit schedules, the site investigator can access the IVRS/IWRS in an earlier visit; and the system will assign the patient a new 28-day randomized treatment study phase IP kit containing an additional 7-day supply of IP.
- 12. Study Day in Table 2 is for the 28-day randomized treatment study phase.
- 13. Targeted physical examination will be conducted on Days 1, 15, 29, and Day 35 (EOS) during the 28-day randomized treatment study phase, please refer to Section 5.2.2.

4.1 **Optional Pre-screening period (Visit 1)**

The Pre-screening visit is optional. Study procedures will be performed according to the Study Plan in Table 1.

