5.1 Efficacy assessments

5.1.1 Blood potassium

Blood samples for determination of potassium will be taken at the times indicated in the Study Plan (see Table 1 and Table 2). Potassium samples will be analyzed locally using i-STAT devices, and serum samples will be prepared and shipped to Central Laboratory. All serum samples should be examined and any hemolyzed samples MUST be redrawn. In the event that hemolysis or other artefacts are suspected based on the reported i-STAT result the sample may be re-drawn to confirm the result. Only the confirmatory sample result needs to be reported in the eCRF.

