Section 3.3.2.1	04-Apr-2022	Updated/added hypotheses for exponential rate of change.	No	Defining two time points (24/48 hr) as not all subjects will have 48h time point	
Section 3.3.3	04-Apr-2022	Table 2 (Analysis visit windows) updated.	Yes		
Section 3.3.5	22-Apr-2022	Section added to summarise how to handle missing S-K data	Yes	Consistency in how this handled for all efficacy outcomes.	
Section 4	04-Apr-2022	Removed quartiles from summary statistics	Yes	Quartiles are not required for the summaries.	
Section 4.1.5	04-Apr-2022	Serum potassium added as a baseline characteristic	NA	To improve assessment of baseline characteristics	
Section 4.1.7.1	04-Apr-2022	Definition of prior and concomitant added. Updated imputation of missing dates to coincide with Section 3.3.1.3	Yes	Clarifying the definition for consistency in outputs and summaries.	
Section 4.2.1.3	04-Apr-2022	Adding a time constraint to imputing missing values with i-STAT	Yes	Add an additional rule as to when it is appropriate to impute value.	

		Information added for the seed, number of burn-ins and variance structure for the multiple imputation		To provide further details on how the multiple imputation should be carried out.
Section 4.2.1.5	04-Apr-2022	Supplementary analysis of primary endpoint updated to be stop date of disallowed medication + 7 days.	Yes	To align the supplementary analyses for disallowed medications.
Section 4.2.1.6	04-Apr-2022	Added a specification of the number of observations required to conduct the subgroup analyses	Yes	To ensure enough observations to generate robust estimates.
Section 4.2.3.6	04-Apr-2022	Updated handling of missing data to be in line with the primary end point.	Yes	Clarifies that all RTP endpoint should be based on the imputed data.
Section 4.3.2	04-Apr-2022	Removed summary of AEs leading to discontinuation and most common AEs. Removed study specific AEs. Added summary by decreasing frequency.	Yes	To removed summaries of AEs that are not required and to update the AE table to present by decreasing frequency rather than selecting the most common to give a most robust overview of AEs.
Section 4.3.3	04-Apr-2022	Removed Hy's Law definitions and updated the elevated liver test summary	Yes	To condense the overview of elevated liver tests.
Section 4.3.6	04-Apr-2022	Added baseline versus maximum on-treatment summary for vital signs.	Yes	To provide additional analyses of the vital signs.

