3.3.1 General Study Level Definitions

3.3.1.1 Definition of Baseline Efficacy Baseline

For the OLP: The baseline Serum Potassium (S-K) will be established on the OLP Study Visit 3 (pre-dose) by taking the mean of 2 different S-K values.

For the RTP: The baseline S-K, S-Aldo and P-Renin will be established based on the last prerandomization measurement for S-K, S-Aldo and P-Renin, respectively, obtained during the OLP.

If baseline S-K C-lab values are missing, the i-STAT data will be used to replace them as described in Section 4.2.1.3. Subjects with missing values at baseline will be excluded from the relevant efficacy analysis.

Safety Baseline

Safety analyses will be performed separately for OLP and RTP. For change from baseline tabulations (laboratory measurements, vital signs, ECG and weight) the baseline will be defined as follows:

For OLP: Baseline will be the last non-missing measurement taken prior to first IP administration during OLP. If a measurement was taken on the date of first IP administration and no time is recorded, it is assumed that the measurement was taken pre-dose and will be considered a candidate for baseline.

For RTP: Same as OLP baseline, i.e. the last non-missing measurement taken prior to first IP administration during OLP.

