4.2.1 Primary Endpoint

The primary efficacy variable is serum potassium [S-K] level during the RTP, Days 8-29, using c-lab, or adjusted i-STAT for visits where c-lab is not available.

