4.2.1.3 Handling of Dropouts and Missing Data

The S-K levels used for the primary analysis will be based on the c-lab measurements obtained during the RTP. Missing S-K c-lab values will be replaced as described in Section 3.3.5.

For the supplementary analysis aimed at evaluating the impact of usage of disallowed medications, if a subject is missing both the central laboratory and i-STAT values they will be imputed using multiple imputation (MI). Note that MI will not be used for the main analysis, as it is expected that, after i-STAT imputation, the amount of missing data will be minimal, and the missing pattern will be MAR, and would be sufficiently explained by the covariates included in the model.

Multiple imputation for the supplementary analysis

Multiple imputation (MI) will be done where imputation of unavailable c-lab values with i-STAT values not possible.

Missing S-K values will be imputed using the Fully Conditional Specification (FCS) method (Brand 1999; Van Buuren 2007). The covariates to be included in the imputation model are; the available c-lab data obtained post randomization visit (RTP Day 1) with baseline

covariates for the open-label initial phase eGFR, the open-label initial phase S-K values, the 28-day randomized treatment study phase S-K values as well as age (<55, 55-64, >64 years), baseline binary indicators for RAAS inhibitors, chronic kidney disease, heart failure, diabetes and treatment arm. The imputation will be performed using the log-transformed S-K values. M=100 will be chosen as the number of imputed data sets, the seed will be set as 22438 and the default 20 burn-ins will be used. An unstructured marginal covariance structure will be assumed. If the specified model fails to converge, alternative structures will be used as described in Section 3.3.6.

Analysis:

Once M complete data sets have been constructed using MI, the statistical analysis will be conducted on each of the M complete data sets. Explicitly, a linear mixed models will be applied, see Section 4.2.1.4.

Pooling:

Rubin's rules will be implemented for combining estimates and standard errors across the imputed data sets and conducting the analysis. Suppose \hat{Q}_i and \hat{W}_i are the point and variance estimates from the ith imputed data set, i = 1, 2, ..., 100. Then the combined point estimate for Q from multiple imputation is the average of the 100 complete-data estimates:

$$\bar{Q} = \frac{1}{100} \sum_{i=1}^{100} \hat{Q}_i$$

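### The 15-minute rule in SAP 3.3.5 is not confined to missing central values, so read literally it blanks observed serum potassium; the fix is one sentence and the expected effect is small

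*SAP*

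**What the plan says.** SAP 3.3.5 has three parts.

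- It opens with the general principle: "The S-K levels used for all analyses will be based on the central laboratory (c-lab) measurements".
- It then allows i-STAT, adjusted by the average paired difference, to replace central values that are missing.
- It ends with the time rule: where the gap between the central and "i-STAT measurements is greater than 15 minutes, the SK measure for that time point will be set as missing".

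The second part carries the condition that the central value is missing. The third does not.

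Elsewhere the plan is consistent. SAP 4.2.1 defines the primary variable as serum potassium "using c-lab, or adjusted i-STAT for visits where c-lab is not available". SAP 4.2.1.3 says "Missing S-K c-lab values will be replaced as described in Section 3.3.5", and SAP 4.2.2.3 and 4.2.3.6 use the same cross-reference. For baseline, SAP 3.3.1.1 says "If baseline S-K C-lab values are missing, the i-STAT data will be used to replace them", pointing to 4.2.1.3, and excludes patients whose baseline is still missing from the analysis concerned. Protocol 8.5.1 uses all available values, replaces only missing central data, and sets no time limit. The SAP amendment history describes the April 2022 change to 4.2.1.3 as "Adding a time constraint to imputing missing values with i-STAT".

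On sampling, Protocol Table 2, note 6, says: "All potassium samples are analyzed by i-STAT and by the Central Laboratory on all occasion".

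**The concern.** A time difference between two measurements most naturally exists where both were taken. Since both assays are planned at every potassium visit of the randomized phase, the rule as worded could apply at any of those visits, including where a valid central result is in hand. It would then remove the better measurement because the poorer one was taken at a different time.

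A gap over 15 minutes is possible. Protocol 5.1.1 lets a sample be redrawn when the i-STAT result looks suspect, with no time limit, and adds "Only the confirmatory sample result needs to be reported in the eCRF". It does not say whether the central tube is redrawn too. At the randomization visit the i-STAT result decides eligibility, and the chemistry sample that includes serum potassium is listed among the procedures that follow (Protocol 4.3.2 and 4.3.4). These passages show that gaps can occur, not how often.

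At stake is whether two programmers who both follow 3.3.5 would build the same data set. Under the literal reading, values drop out of the primary comparison (tests 2-3), Day 29 normokalemia (4-5), the normokalemic day count (6-7) and time to hyperkalemia (8-9).

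**Working it through.** **Inputs from the documents.** 250 patients, 100:100:50; difference 0.30; SD 0.50; two-sided 5% (Protocol 8.2). Seven visits on Days 8, 12, 15, 19, 22, 26 and 29 (Protocol Table 2). **Assumed, because not given:** the rate of gaps over 15 minutes and the within-patient correlation (0.3-0.7).

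**1. The plan's own power.** Noncentrality = 0.30 / (0.50 × √(1/100 + 1/50)) = 0.30 / 0.0866 = 3.464 on 148 df. Noncentral t power = 0.931, which agrees with the stated figure of more than 90%.

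**2. How many values the literal rule could touch.** 250 × 7 = 1,750 Day 8-29 values. Gaps at 2%, 5% or 10% of visits blank 35, about 88 or 175 of them, and 5, 12-13 or 25 of the 250 Day 29 values.

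**3. Random loss of visits.** Take 0.50 as the SD of the seven-visit patient mean, with equal correlation ρ between visits. With m visits left, m being binomial(7, 1 − loss rate) and at least 1, the variance ratio is

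R = (ρ + (1 − ρ)·E[1/m]) / (ρ + (1 − ρ)/7).

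Step 1 is then repeated with SD 0.50 × √R.

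| Visits lost | ρ = 0.3 | ρ = 0.5 | ρ = 0.7 |
|---|---|---|---|
| 10%: R | 1.033 | 1.017 | 1.008 |
| 10%: power | 0.923 | 0.927 | 0.929 |
| 30%: R | 1.138 | 1.069 | 1.032 |
| 30%: power | 0.897 | 0.914 | 0.923 |

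**4. Loss confined to high values.** A simulation blanked 20% of visits at 5.1 mmol/L or above (single-visit SD 0.5, correlation 0.5, placebo mean 0.30 above ZS). The difference shrank from 0.299 to 0.284 with a ZS mean of 4.5, and from 0.300 to 0.289 with a ZS mean of 4.7. All of these settings are assumptions.

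**5. Loss of patients through a blanked baseline.** Step 1 with fewer patients:

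| ZS v placebo | Power |
|---|---|
| 95 v 47 | 0.916 |
| 90 v 45 | 0.904 |
| 89 v 44 | 0.898 |

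The last row loses 150 − 133 = 17 of 150 patients, or 11.3%.

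**6. Day count for one patient.** With all seven visits normal, the interval rule in SAP 4.2.3.3 gives 29 − 8 = 21 days and the period rule in 4.2.3.2 gives 29 − 8 + 1 = 22. Now let Day 15 alone be abnormal:

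- interval rule: (12 − 8) + (29 − 19) = 14;
- period rule: (12 − 8 + 1) + (29 − 19 + 1) = 16.

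If that value is blanked, 4.2.3.2 and 4.2.3.6 bridge the gap and the count returns to 21 or 22, a gain of 7 or 6 days. The neighbours of each of the five interior visits are 7 days apart, so the gain is the same for all five. For Day 8 (17 or 18 days) or Day 29 (18 or 19 days) the count does not change.

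**7. Time to hyperkalemia.** If a first value of 5.1 or above on Day 12 is blanked and the Day 15 value is also high, the event moves from day 12 to day 15. If no later value is high, the patient is censored at the last measurement. The documents give nothing from which to size this.

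**The case against.** The strongest reply is that the SAP already settles the intent. The section is about missing data, the sentence before the rule is conditional on a missing central value, the amendment log calls the rule a constraint on imputing, and every other section invokes 3.3.5 only for missing central values. A programmer would have to set all of that aside to delete an observed result. The narrow reading also works in practice: a central sample can be drawn and timed and still yield no result, so a gap can be computed when the value is missing. This stands, and it is why deletion cannot be called an established effect.

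The repeat i-STAT required before a dose change or discontinuation comes 10 ± 2 minutes after the first, so at most 12 minutes. If the central tube was drawn with the first sample, that repeat alone does not breach the limit. This stands too.

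The day-count gain comes from the bridging rules, which act on any missing visit. That is correct; the literal 15-minute rule would only feed them visits that were not missing. The i-STAT sensitivity analysis in SAP 4.2.1.5 gives some cross-check, but only on the primary endpoint, not on tests 4-9.

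A reader might infer that the trial will discard observed central data, or that its power is in doubt. The documents support neither. They give no gap rate, and random visit loss hardly moves power. Nor does a blanked baseline always remove a patient: the open-label baseline averages two values, and the randomized-phase baseline is the last measurement before randomization, so an earlier value might be used.

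What remains is that no sentence says an observed central value is kept, while one sentence, as worded, says it is not.

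**Conclusion.** Wrong as written, with a small expected impact. Taken literally, the rule contradicts the opening of 3.3.5, SAP 4.2.1 and Protocol 8.5.1; the surrounding text shows that only a limit on i-STAT replacement was meant.

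The size is unknown because the frequency of gaps is unknown. Under the stated assumptions, random loss of 10% of visits costs primary power about one percentage point or less, and even 30% leaves it at about 90% or above. Loss limited to high values would pull the treatment difference slightly towards zero. The consequences to guard against are exclusion through baseline, with 90% power lost at about 11-12% of patients, and the conversion of observed abnormal or hyperkalemic values into normokalemic days or later or censored events. The 6-7 days are for one patient with one such visit, not a treatment-group effect.

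**What to change.** Replace the last sentence of SAP 3.3.5 with:

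> The 15-minute limit applies only to replacement of missing c-lab values: when c-lab is missing, an i-STAT value taken more than 15 minutes from the recorded c-lab collection time is not substituted and S-K stays missing. Observed c-lab values are always retained.

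The sections that refer to 3.3.5 then need no edit. The cost is one wording change and a check that the derivation program follows it. Sample size, alpha and planned power do not change. The trade-off is that central values whose paired i-STAT was drawn more than 15 minutes away stay in the analysis, which is what SAP 4.2.1 already calls for.
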